How does task loading in a PICU environment impact on clinician situational awareness and awareness of the passage of time?

NCT number: ID not yet assigned

Date: 1 Dec 2021

STUDY INVESTIGATORS

- Principal Investigator (A): [name]
 - Email: [contact]
- Principal Investigator (B): [name]
 - Email: [contact]
- Principal Investigator (C): [name]
 - Email: [contact]

1. PICU, Great Ormond Street Hospital, London, UK
2. Attention & Cognitive Control Group, University College London

INTRODUCTION

There is little published literature on the subject of clinician perception of trends in patient observations on PICUs (Paediatric Intensive Care Units) and how this situational awareness is impacted on by clinical tasks. Human factors training cautions against the loss of situational awareness and time perception but there is no supporting observational data in the IC (Paediatric Intensive Care) setting.

Perceptual loading theory hypothesises that, under low load situations, awareness extends to environmental features not directly related to the task at hand. However in high load situations awareness is restricted to the object of focused attention. Individuals experience different load from a given task depending on their skills and experience.

Our pilot project intends to examine how clinician perception is affected by task loading. In our protocol two tasks are undertaken. The administrative task involves requesting a list of investigations from a clinical guideline. The technical task is the uncomplicated insertion of a central venous catheter (CVC) into a simulated vein. In each case we will record proxies for perception: awareness of the passage of time, the time point at which monitoring changes are noted and retrospective recall of observation trends. Our protocol was designed with psychology input from [name], group leader of the UCL Attention & Cognitive Control laboratory.

Passage of time is measured by the participant pressing a foot pedal linked to timing software at every perceived 10 second interval of elapsed time. A retrospective estimate of total elapsed time will also be recorded. After the second task, immediate verbal questions are asked followed by a written questionnaire which contains questions targeting the participant's awareness of monitoring changes.

Analysis will involve paired t testing of the timing interval and observation trend data to see if task loading significantly impacts accuracy.

BACKGROUND

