 - The blood pressure will fall from an initial systolic/diastolic (mean) of 90/50 (63) at 30 seconds to 75/48 (55) at 4 minutes and then remain static at that level. There will be no alarm. This gradual drift tests participants' awareness and identification of monitoring trends during the task through what point they notice a change, if they do at all.

- Other parameters (heart rate, respiratory rate, oxygen saturations, end-tidal CO₂ and temperature) will not vary.
- Scenario B
 - The oxygen saturation measure will fall to 88% for 5 seconds at 30 seconds into the task, triggering an alarm. This is to orient the participant to the monitor being part of the environment.
 - The blood pressure will rise from an initial systolic/diastolic (mean) of 75/48 (55) at 30 seconds to 90/50 (63) at 4 minutes and then remain static at that level. There will be no alarm. This gradual drift tests participants' awareness and identification of monitoring trends during the task through what point they notice a change, if they do at all.
 - Other parameters (heart rate, respiratory rate, oxygen saturations, end-tidal CO₂ and temperature) will not vary.

End point:

6 minutes or completion of the task.

The participant will be asked for the time period they believe has elapsed between the first pedal press and the last.

3. Technical task

Inserting a CVC.

Equipment required:

- Child mannequin, intubated
- CVC insertion mannequin
- US machine + gel + probe cover
- CVC set
- Syringes, flush
- Cleaning- chlorprep lollipops
- Suture, needle holders, scissors, sharps bin
- Dressings + biopatch
- Gloves (non-sterile)
- Drape
- 5 +10ml syringes
- Sterile field drape
- Pen and paper for documentation
- Simulated bedside monitor
 - Varies observations over time in line with preset programming determined by the study team
- Foot pedal and data recorder for time logging

Setup

All equipment laid out on a table. The tissue pad is attached to the mannequin leg and surgically draped appropriately. The ultrasound probe is already in a sterile sheath, lying on the sterile field.

Instructions to subject

You are the fellow/consultant looking after Sophie. Sophie is a 2 year old girl with PIMS-TS who requires central access for inotropes. She is intubated and is stable on minimal ventilation and peripheral noradrenaline of 0.1mcg/kg/min. This is the Sophie's bedspace, all the equipment you see is part of the simulation

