You have been asked to insert a femoral CVC and have already prepared your equipment.. The line is not flushed. You are already wearing the appropriate sterile gown. Please only use steristrips and dressings, with no sutures, to secure the line to the mannequin. Please document the procedure on the paper provided when you have completed insertion of the line.

I am the nurse in the next bedspace, if at any point you want to make a clinical intervention please continue with the task and verbalise anything you would like me to do.

As before, from when I ask you to begin, please press the foot pedal every 10 seconds, trying to be as accurate as possible. The task will last for several minutes.

Given that this is a simulated mannequin please take all the time you need to familiarise yourself with the ultrasound appearance of the vessels before telling me you are ready to begin.

Events during the task:

Same as for the administrative task.

End point

6 minutes or completion of task documentation.

At the end of the task, progress through the checkpoints below will be noted by the experimenter:

1. Equipment preparation / line flushing
2. Cleaning of the procedure site
3. Initial ultrasound scan
4. Needle manipulation
5. Guide wire insertion
6. Tract dilation
7. Line insertion
8. Line suturing
9. Line dressing
10. Documentation completed

The participant will be asked for the time period they believe has elapsed between the first pedal press and the last.

Post- task review

Following completion of the second task the participant will immediately be asked the following questions:

“Did you see anything of note on the monitor aside from the desaturation” - their yes/no answer is recorded.

“If there were changes in the blood pressure did you notice a fall or a rise” - their rise/fall answer is recorded.

Was the extent of the fall/rise in systolic pressure: 5, 10,15, 20 or 25 mmHg- their selection is recorded.

Which of the tasks did you find more challenging? And why?

They are then asked to describe their subjective experience- “how were those tasks for you?”

They are then asked- “How would you describe your familiarity with EPIC order requesting?”- Very, somewhat, limited, none

They are then provided with the questionnaire from the appendix.

Measurement tools used

- For each experimental run there are 2 variables
 - The task order- administrative or technical completed first

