 - The trend in monitored observations- increasing or decreasing blood pressure in the second task

The following parameters are measured during both tasks:

- Timestamps of foot pedal use by the participant
- Retrospective recall of total elapsed time
- Time to complete task/progress at experiment end
- Question responses

Following completion of the tasks the data collected can be analysed as below.

Time interval analysis:

- Intervals between pedal presses are extracted for each scenario (timing control/administrative/technical tasks)
 - Derive: min/max/mean/interquartile range/standard deviation for each case
- Comparison of the individual’s retrospective perceived elapsed time with actual elapsed time. Reported as percentage error of actual elapsed time.

This will allow the following results to be reported:

- Mean deviation for each individual from their baseline in each of the tasks.
- Change in retrospective perceived elapsed time compared to actual elapsed time.
- Distribution of timing in the control task for each individual.
- Paired t-test comparison to test if there are significant differences in time interval distribution for each individual between control, administrative and technical tasks.
- Overall proportion of participants showing significant deviation from their own baseline in each of the administrative and technical tasks
- Population limits/mean
- Comparison of the mean perceived time interval between subgroups
 - By task order

- By time within task (split into thirds- 2 minutes each)
- By grade
- By number of CVCs previously inserted
- By first 25% vs last 25% of participants

Monitor trend perception analysis:

Each participant will provide question answers from immediately after the second task.

This will allow the following results to be reported:

- Rationale
 - The first question “Did you see anything of note on the monitor” is chosen to highlight inattentive blindness and is asked immediately to avoid any impact from the role of memory or priming from other questions asked.
 - This will be reported as proportion who noted a change
 - The subsequent questions are asked to elicit responses from those who observed the trend but are not sufficiently confident in their recall to report it.
- From the responses the following can be derived:
 - Correct identification of the blood pressure trend- reported as proportion of participants correct

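### The technical run continues through note-writing with no time recorded for the switch, so fast operators' pedal intervals mix procedure with paperwork and the experience comparisons become hard to interpret

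*Combined protocol and SAP*

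**What the plan says.** The Introduction describes the condition in these words: "The technical task is the uncomplicated insertion of a central venous catheter (CVC) into a simulated vein". The Background presents the two tasks as coming from different domains, administrative and technical.

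The section on the technical task adds a written component. Its instructions say "Please document the procedure on the paper provided when you have completed insertion of the line", its end point is "6 minutes or completion of task documentation", and the tenth and last checkpoint is completed documentation. The administrative task ends at "6 minutes or completion of the task". In both tasks the participant is asked to "please press the foot pedal every 10 seconds, trying to be as accurate as possible" throughout.

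On recording, the technical end point section says "At the end of the task, progress through the checkpoints below will be noted by the experimenter". The list of measured parameters adds completion time or progress at the end of the experiment. No time is logged for the change from line work to writing.

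On analysis, the time interval section says "Intervals between pedal presses are extracted for each scenario (timing control/administrative/technical tasks", with no rule for writing presses. The only split within a run is "By time within task (split into thirds- 2 minutes each", which follows the clock and not the activity. Mean interval is then compared by grade and by number of lines previously inserted. The impact of experience is the stated secondary outcome.

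**The concern.** What the technical label covers depends on the participant's speed. Someone still working on the line at 6 minutes supplies a record of procedure alone. Someone who has dressed the line supplies procedure followed by handwriting, pooled under one label.

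Speed plausibly goes with grade and with the number of lines inserted, which are the factors used to study experience. A smaller technical effect in experienced clinicians could mean that they withstand the load better, or that more of their record is paperwork. The planned data cannot tell these apart. In a hypothesis-generating pilot, that signal is one that would be carried forward. The average contrasts that use the technical run (against control and against the administrative task) would also be diluted to some degree if writing is the lighter activity.

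**Working it through.** The plan gives no effect size, standard deviation or sample size calculation, so there is no figure of its own to reproduce. What follows is illustrative.

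**From the documents:** maximum run 360 s; target interval 10 s, hence 360/10 = 36 nominal intervals; blood pressure drift from 30 s to 240 s, in the second task only.

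**Assumed:** writing time d of 30 to 120 s; intervals during writing equal to those in the administrative task, taken as 10 s; line-work intervals of 10 + δ seconds, with δ from 1 to 4. The sign of δ is also an assumption.

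**Share of the run.** 30/360 = 8% and 120/360 = 33%, or about 3 to 12 nominal intervals.

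**Retained contrast for one participant.** With run length T, the observed mean interval is T / [(T − d)/(10 + δ) + d/10], and the retained share is r = (observed mean − 10)/δ.

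- Low end, T = 360, d = 30, δ = 1: 360/(330/11 + 3) = 360/33 = 10.91, so r = 0.91.
- High end, T = 360, d = 120, δ = 4: 360/(240/14 + 12) = 360/29.14 = 12.35, so r = 2.35/4 = 0.59.

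| Run T (s) | Writing d (s) | Time share | r, δ = 1 | r, δ = 2 | r, δ = 4 |
|---|---|---|---|---|---|
| 360 | 30 | 8% | 0.91 | 0.90 | 0.89 |
| 360 | 60 | 17% | 0.82 | 0.81 | 0.78 |
| 360 | 120 | 33% | 0.65 | 0.62 | 0.59 |
| 300 | 60 | 20% | 0.78 | 0.77 | 0.74 |
| 240 | 60 | 25% | 0.73 | 0.71 | 0.68 |

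The loss slightly exceeds the time share, because a mean of intervals weights by presses and the shorter writing intervals supply more presses per second.

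**Experience comparison.** A participant who never reaches documentation keeps 100%, so the gap between two participants with the same true effect is 1 − r, or 9% to 41% of that effect. Between groups, the gap is multiplied by the difference in the proportions reaching documentation. If these were 75% and 10% (assumed), it would be 0.65 × 9% = 6% to 0.65 × 41% = 27%.

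**Average contrast.** If a proportion q reaches documentation, the retained share is 1 − q(1 − r). With q = 10% and r = 0.91 this is 1 − 0.10 × 0.09 = 99%. With q = 75% and r = 0.59 it is 1 − 0.75 × 0.41 = 69%. With q = 0 it is 100%.

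**Interval SD.** Take T = 360, d = 60, δ = 2. The run holds 300/12 = 25 line-work intervals and 60/10 = 6 writing intervals. Mixing them adds a between-segment variance of (25/31)(6/31)(2²) = 0.62 s². If the SD within each segment is the same, the run SD rises; if writing is steadier, it may fall. The direction is therefore not determined.

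**Trend outcome.** Writing overlaps the drift only if it starts before 240 s. A run ending at 240 s with 60 s of writing overlaps 60 s of drift. Writing that starts later meets only the static final value.

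**The case against.** Documentation is deliberately the last step of the task, so it can be argued that the whole run is the intended condition and that this is a choice of estimand. That is a fair position, but the plan's stated interest is in whether one practitioner can insert a line and stay aware. The whole-run result can be kept beside the restricted one.

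It is also unknown whether anyone gets that far. Flushing, cleaning, scanning, needling, wire, dilation, insertion and dressing must all fit within 6 minutes. Against that, the site is already draped, the probe sheathed and the gown on, sutures are not used, and ultrasound familiarisation precedes the start. The end point itself allows for completion. Frequency remains open.

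Existing data help in part. The checkpoints show who finished dressing, which permits a sensitivity analysis without those participants, and writing that begins after 4 minutes falls wholly in the last third. Neither locates the writing presses, and leaving out finishers removes the fastest operators.

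Two stronger readings are tempting. A reader might infer that experience confounds the task contrast itself. It does not: the timing comparison is paired within person, and the trend comparison is by randomised task order, stratified by role. A reader might also infer that both alternative hypotheses are pulled towards no difference. The documents do not support that. The Background says only that administrative work might be expected to be less loading and does not extend this to handwriting a note. The direction for the interval SD is open, and the drift is over by 4 minutes.

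**Conclusion.** The point holds in a limited form. Note-writing lies inside the technical run, its intervals are pooled with line work, and nothing planned records when it starts. The comparisons of mean interval by grade and by line count may therefore partly reflect who reached the paperwork.

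The size is unknown. Under the assumptions above, an affected participant keeps 91% to 59% of the mean-interval contrast; with no participant reaching documentation the loss is zero. The dilution depends on writing being less loading than line insertion, and the experience bias further depends on speed going with experience. Effects on the interval SD and on trend awareness are not established. This is a cheap improvement to a pilot and does not invalidate the design, but the missing time cannot be recovered after the runs.

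**What to change.** - Have the experimenter, who already notes the checkpoints, mark on the data recorder the moment line dressing (checkpoint 9) ends.
- Report the technical-task interval mean and SD twice: for the whole run, and for presses up to that mark or 6 minutes, whichever comes first. Do the same in the grade and line-count comparisons. Describe writing presses separately.
- Because the restricted window is shorter for fast operators, also compare the tasks over a common early window, such as the first two of the planned thirds (0 to 4 minutes).
- For the trend outcome, keep all participants as randomised and only state how many began writing before 4 minutes. Excluding them would remove fast operators from the technical-second group alone and create an imbalance in speed, and probably in experience.

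The cost is one extra mark per run, a few lines of analysis text, and fewer technical intervals for fast operators in the restricted analysis: 90/10 = 9 of 36 nominal intervals if writing starts at 4:30. The retrospective estimate of elapsed time covers the whole run and cannot be divided by the mark.

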 - Correct identification of no trends in other parameters - reported as proportion of participants correct
 - Accuracy of magnitude recall
 - The blood pressure either falls or rises between a systolic/diastolic (mean) of 70/48 (55) and 90/50 (65).
 - From the position of the x on the linear blood pressure scales we can derive:
 - The accuracy of the initial and final estimates compared with the actual values- reported for each task as the population mean and standard deviation of the percentage errors compared with the actual value.
 - The accuracy of the magnitude of the change, determined through comparing the difference in the estimated initial and final values compared with the actual 20mmHg systolic/ 10mmHg diastolic change for each task. The population mean and standard deviation of the percentage errors compared with the actual change will be reported for each task.
 - We hypothesised that there would be a priming effect following administration of the questionnaire, with participants more likely to attend to blood pressure trends if the questions were asked prior to the second task. We will therefore only ask the questions after the second task. We can then compare between the subgroups, split by which of the tasks was performed second to examine the impact of task type.
 - i.e the questionnaire analysis will have half the n of the overall study
- For the above we can compare subgroups using Fishers exact test.
 - By task order
 - By grade
 - By number of CVCs previously inserted

- By first 25% vs last 25% of participants

STATISTICAL CONSIDERATIONS AND DATA ANALYSIS

Sample size and statistical power

This is a pilot study and as such we do not expect it to be adequately powered to confirm hypotheses but intend that it should be hypothesis generating.

Statistical methods

The population summary statistics detailed above will be calculated using 'SPSS statistics' software with built-in min/max/mean/IQR/SD calculation.

With assumed normally distributed timing data and each participant completing 2 tasks the distributions will be compared with a paired sample t-test for; control vs administrative, control vs technical and administrative vs technical. For subgroup analysis paired or unpaired sample t-tests will be used as appropriate in each case. For the trend perception outcomes, contingency tables will be created for each subgroup and compared using Fishers exact test.

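### Change recall is scored against one fixed pressure change, although a second task may end on completion before the drift settles at 4 minutes

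*Combined protocol and SAP*

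**What the plan says.** Both loaded tasks carry a completion clause. The administrative task ends at "6 minutes or completion of the task" (Experimental scenarios, 2. Administrative task, End point) and the technical task at "6 minutes or completion of task documentation" (3. Technical task, End point). The timing control has a fixed length of 6 minutes. Both kinds of ending are foreseen, because "Time to complete task/progress at experiment end" is listed among the recorded measures (Measurement tools used).

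The pressure drifts in the second task only. In scenario A, systolic/diastolic (mean) goes from "90/50 (63) at 30 seconds to 75/48 (55) at 4 minutes and then remain static at that level". Scenario B reverses this, from "75/48 (55) at 30 seconds to 90/50 (63) at 4 minutes and then remain static at that level".

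Under Monitor trend perception analysis, the recalled change is "compared with the actual 20mmHg systolic/ 10mmHg diastolic change for each task". The same section compares initial and final estimates with the actual values, without saying what these are for a run that ended early. Under Time interval analysis, one subgroup split is "By time within task (split into thirds- 2 minutes each".

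The protocol gives no minimum task duration, no statement that the monitor runs on after completion, and no scoring rule for a run that ends before 4 minutes.

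**The concern.** How much of the drift a participant sees depends on when the second task ends, but the reference for the change score does not. Anyone who finishes before 4 minutes is marked down for failing to recall a change that was never displayed. Recall of monitor trends is one of the two primary outcomes, and magnitude accuracy is part of it.

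There is a second consequence. Trend recall is compared between participants, split by which task they did second. If early completion is more common in one task, that group has seen less drift on average, and the contrast bearing on H_B mixes task type with exposure. This reaches the proportions noticing a change and naming its direction as well as the magnitude score, because a shorter and smaller drift is harder to notice.

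The fixed 2-minute blocks raise a lesser version of the same issue: short runs leave the later blocks partly or wholly empty.

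**Working it through.** **1. The plan's own figures.** 6 min / 3 = 2 min per third, which holds only for a full 6-minute run. The scenario descriptions give a systolic change of 90 - 75 = 15 mmHg, diastolic 50 - 48 = 2, mean 63 - 55 = 8. The scoring section states a range of 70/48 (55) to 90/50 (65), that is, systolic 20, diastolic 2, mean 10. Its 20 mmHg systolic therefore follows from its own range but not from the scenarios. Its 10 mmHg, labelled diastolic, equals the difference in means.

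**2. Share of the drift shown.** The drift runs from 30 s to 240 s. Assumption: it is linear, since the protocol calls it only gradual. For a stop at t seconds (30 ≤ t ≤ 240):

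share = (t - 30) / (240 - 30); systolic change shown = 15 × share.

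**3. Score of a participant with perfect recall.** Error = change shown / reference - 1. Against the programmed 15 mmHg this is share - 1, the part due to early stopping alone. The last column uses the 20 mmHg reference and so adds the separate mismatch.

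| Stop | Share | Shown (mmHg) | Error vs 15 | Error vs 20 |
|---|---|---|---|---|
| 120 s | 90/210 = 0.429 | 6.4 | -57% | -68% |
| 150 s | 120/210 = 0.571 | 8.6 | -43% | -57% |
| 180 s | 150/210 = 0.714 | 10.7 | -29% | -46% |
| 210 s | 180/210 = 0.857 | 12.9 | -14% | -36% |
| 240 s or later | 1 | 15 | 0% | -25% |

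The stopping times are illustrative; the documents give no completion times.

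**4. Final value, if it too were scored against the settled value.** At 180 s scenario A shows 90 - 10.7 = 79.3, and 79.3/75 - 1 = +5.7%. Scenario B shows 75 + 10.7 = 85.7, and 85.7/90 - 1 = -4.8%. The signs are opposite, so pooling the scenarios would partly hide the error.

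**5. Seconds contributed to each 2-minute block.** A 3-minute run gives 120/60/0, a 4-minute run 120/120/0, a 5-minute run 120/120/60 and a 6-minute run 120/120/120. A run of 4 minutes or less adds nothing to the last block.

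**The case against.** The strongest reply is that stops before 4 minutes may hardly occur. The order sheet in the Appendix holds about 52 named requests on 18 lines; finishing by 240 s means one every 240/52 = 4.6 s while also working a pedal. The technical task has ten checkpoints ending in written documentation, and recording progress at the end suggests that many runs will be cut off at 6 minutes. This stands as a limit on how often the problem arises. It does not supply the missing rule for runs that do end early, which the recorded completion time allows for.

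Several stronger readings are tempting but unsupported:

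- A reader might infer that noticing and direction are also scored wrongly. They are not scored against any magnitude; a participant who stops at 180 s and names the right direction is counted correct. Only the opportunity to notice is unequal.
- A reader might infer that the final-value score is certainly wrong. The actual values could already mean what was on the screen at the end. The fixed change cannot be read that way.
- A reader might attribute the whole -46% at 180 s to early stopping. A full 6-minute run with perfect recall already scores 15/20 - 1 = -25%, from the mismatch alone.
- A reader might infer that experienced clinicians finish faster and are penalised. The documents give no link between speed and experience.
- A reader might see different completion rules in the two tasks. Documentation is the last technical checkpoint, so both rules mean that the whole task is done.

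The study is also a hypothesis-generating pilot, and the thirds are one subgroup split among several. An empty last block loses data there but introduces no wrong reference.

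**Conclusion.** The concern holds for the change score: as written, it mis-scores any participant whose second task ends before 4 minutes. From early stopping alone the error is -29% at 180 s and -43% at 150 s. These figures assume a linear drift, that the earlier of 6 minutes and completion ends the task (the natural reading, though not spelled out), and that the display stops counting at that point. They do not depend on whether the programmed change is 15 or 20 mmHg, provided the same figure serves as reference.

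The number affected is unknown and may be small. Mixing of exposure with task type is conditional: it arises only if early stopping differs by the task performed second. The point merits a change because a primary outcome is touched and the correction costs little, not because large bias has been shown.

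**What to change.** 1. Score the recalled change and final value against what the monitor displayed when that participant's second task ended, derived from the recorded completion time and the preset monitor programme. Perfect recall then scores 0% at any stopping time.
2. Report task duration, and the number stopping before 4 minutes, by task.
3. Individual references repair only the magnitude score. For noticing and direction, add a sensitivity analysis limited to participants whose second task lasted at least 4 minutes, noting that this conditions on completion speed.
4. Keep the fixed 2-minute blocks, which stay aligned with the clock-timed monitor events and the 6-minute control, and report how many participants contribute to each. Thirds of each person's own duration would lose that alignment.
5. Separately, reconcile the 15 mmHg systolic change in the scenarios with the 20 mmHg in the scoring section, along with the diastolic and mean figures.

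Items 1 to 4 need only analysis-plan wording, and the data are already collected. The small downside is individual rather than fixed reference values. Running monitor and pedal on to 6 minutes after completion is not recommended: it changes the procedure and gives finishers unloaded time facing the monitor, which blurs the awareness under load that the study aims to measure.
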